### **8.8.2 Secondary Endpoint**

*Secondary Endpoint:* Secondary endpoints include:

#### **Incidence of Surgical Site Infections**

The incidence of surgical site infections (SSIs) will be recorded for each subject (as occurring within 30 days of treatment). Descriptive statistics will include the total number of infections. Comparative analysis between treatment groups will be conducted using Chi-Square tests or Fisher's exact test if the expected frequencies are low.

### **Cosmesis**

Cosmesis will be assessed using a validated scoring system, such as the Modified Hollander Score. The chosen scale will be detailed in the appendix. Descriptive statistics will include mean, median, and standard deviation of the cosmesis scores. The distribution of scores will be summarized using frequency tables. Comparative analysis between treatment groups will be performed using t-tests or ANOVA for normally distributed data, and Mann-Whitney U test or Kruskal-Wallis test for non-normally distributed data. Additionally, the proportion of subjects achieving satisfactory cosmesis (as defined by a predetermined threshold) will be compared using Chi-Square tests.

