**Description of Study Intervention:**

This prospective study compares the use of OptiClose and Dermabond in the closure of subcutaneous tissue following surgical site incisions. The study has two separate arms. In the first arm, the incision site will large enough to require the use of a mesh, and participants will be randomized into the OptiClose Secure group or the Dermabond Prineo group. In the second arm of the study, the incision site will be small enough not to require a mesh and will use only glue, and participants will be randomized into the OptiClose Rapid group or the Dermabond Advanced group. In both arms of the study, participants will be assessed at three different time points following the surgical procedure: immediately after application following skin closure, and two subsequent visits. These assessments within this study will investigate the cosmesis score, presence of

possible dehiscence or allergic reactions, dry time, and ease of application.

At the conclusion of the final assessment visit (at the end of the final visit), the participants will be dismissed from the study. Participants are free to withdraw from the study, and the principal investigator may also remove the participant if any issues arise that preclude them from continuing.

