## **6. STUDY PROCEDURES AND ASSESSMENTS**

### **6.1 Participant Screening and Informed Consent**

The pre-visit may take up to 30 minutes. Study staff will screen potential participants and obtain informed consent during this time as described in Section 5.

Participants will be randomized depending on the predicted incision size. If the incision site is large enough to require the use of the mesh and glue combination, participants will be randomized into the OptiClose Secure group or the Dermabond Prineo group. If the incision site is determined to be small enough that it does not require a mesh, participants will be randomized into the OptiClose Rapid group or the Dermabond Advanced group.

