### **8.2 Randomization**

The order of products tested first or second will be randomly assigned according to a randomization table developed by the biostatistics team. We will conduct a two-arm, prospective, unblinded, randomized prospective control trial by which participants will be randomly assigned to either receive treatment A: the Dermabond wound closure adhesive or the treatment B: OptiClose wound closure adhesive in participants undergoing the closure of any subcutaneous tissue following surgical site incisions. After assignment to treatment arm per incisional length requirements, participants will be randomized using

simple randomization, with 15 participants designated to receive Opticlose and 15 to receive Dermabond. Participants will be patients undergoing a skin closure of a full thickness surgical incision. For the products tested in this study, a total of 60 participants will be required to complete the study, 30 in each incisional length group. If a participant is unable to complete the study, the participant will be replaced such that the new participant will be assigned to the randomization cohort of the replaced participant.

Enrollment will continue until the study from the evaluable number of participants (60) is completed.

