### **8.7 Statistical Analysis of Study Endpoints**

Statistical analyses will be conducted in SAS® software, Version 9.4 or higher of the SAS System for Windows (Copyright © 2013 SAS Institute Inc.) or other appropriate statistical software.

All continuous variables will be summarized using the following descriptive statistics: n (non-missing sample size), mean, standard deviation, median, maximum and minimum. The frequency and percentages (based on the non-missing sample size) of observed levels will be reported for all categorical measures. In general, all data will be listed, sorted by site, treatment and subject, and when appropriate by visit number within subject. All summary tables will be structured with a column for each treatment in the order (Control, Experimental) and will be annotated with the total population size relevant to that table/treatment, including any missing observations. 95% confidence intervals will be calculated for all means.

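### The cosmesis comparison leaves open how many groups ANOVA or Kruskal-Wallis would cover and has no incision-length term, although product is randomised only within length group

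*Combined protocol and SAP*

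**What the plan says.** The Cosmesis paragraph of Section 8.8.2 reads: "Comparative analysis between treatment groups will be performed using t-tests or ANOVA for normally distributed data, and Mann-Whitney U test or Kruskal-Wallis test" for non-normal data. Normality is the only selection rule. The paragraph does not give the number of groups, say when ANOVA replaces the t-test, or mention incision length.

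The trial's question is about two brands: "This prospective study compares the use of OptiClose and Dermabond in the closure of subcutaneous tissue following surgical site incisions" (Synopsis, Description of Study Intervention). Allocation is nested in incision length. Section 6.1 says "Participants will be randomized depending on the predicted incision size". Where mesh is needed, "participants will be randomized into the OptiClose Secure group or the Dermabond Prineo group"; where it is not, "participants will be randomized into the OptiClose Rapid group or the Dermabond Advanced group". Section 8.2 gives the numbers in each length group, "with 15 participants designated to receive Opticlose and 15 to receive Dermabond", and the total, "a total of 60 participants will be required to complete the study, 30 in each incisional length group". The design is therefore four cells of 15, with product randomised within length and length itself not randomised.

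Other sections point in different directions on what a treatment group is. Section 8.2 names treatments A and B, Section 8.7 gives the summary tables one control and one experimental column, and the applicator-tube paragraph compares two products. The dry-time paragraph, however, plans post-hoc comparisons across groups, which suggests more than two.

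**The concern.** With two groups, one-way ANOVA repeats the pooled t-test and Kruskal-Wallis repeats the asymptotic Mann-Whitney test. As one-way tests, they add something only with more than two groups, and the only such set of treatment groups in the design is Secure, Prineo, Rapid and Advanced.

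The null hypothesis of a four-product test is that all four groups are equal. It is false whenever large mesh-closed incisions score differently from small glue-only ones, whatever the brand. Two of its three degrees of freedom go to length and to the length-by-brand interaction. A small p-value could then be read as a treatment difference when it reflects incision size, a contrast that was not randomised. The paragraph names no follow-up contrast that would separate the two. Because the trial is unblinded, a choice of test left open until the data are seen is also harder to defend.

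**Working it through.** **Plan's own figure.** There is none for cosmesis. The only power statement (Section 8.1) concerns dry time and is not used here.

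**Inputs.** From Sections 6.1 and 8.2: four cells, n = 15 each, total 60. Assumed, because the documents do not give them: normal scores with common SD σ = 1, two-sided α = 0.05, a length effect L and a brand effect d in SD units.

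**Step 1. Two groups.** On one simulated data set of 30 v 30, ANOVA and the t-test both give p = 0.1759. Kruskal-Wallis and Mann-Whitney (asymptotic, no continuity correction) both give p = 0.1646. With two groups the choice makes no difference.

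**Step 2. One-way F test over four products, brands identical.** Degrees of freedom are 3 and 56, and the critical value is 2.769. The cell means are 0, 0, L, L, so the noncentrality is λ = n Σ(μᵢ − μ̄)²/σ² = 15 × 4 × (L/2)² = 15L².

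| L (SD) | λ | Rejection rate |
|---|---|---|
| 0 | 0 | 5.0% |
| 0.25 | 0.9375 | 10.7% |
| 0.5 | 3.75 | 31.7% |
| 0.8 | 9.6 | 70.9% |
| 1.0 | 15 | 89.6% |

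At α = 0.025 the rates are 22.0% at 0.5 SD and 60.0% at 0.8 SD. Simulated Kruskal-Wallis (5,000 trials per scenario, α = 0.05) gives 29.3% and 66.7% at the same two points.

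**Step 3. Brand contrast within length.** Take b as the mean of the two within-length brand differences. Its variance is (1/4)(2σ²/15 + 2σ²/15) = σ²/15, with 56 df from the four cell means (a main-effects model has 60 − 3 = 57). The length effect cancels. In simulation with identical brands, this contrast rejects 4.3% to 5.4% of the time for L from 0 to 1 SD.

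**Step 4. Power for a real brand effect, L = 0.** The contrast has noncentrality d√15. The F test has λ = 15d², by the same algebra as in Step 2.

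| d (SD) | d√15 | Within-length contrast | Four-product F test |
|---|---|---|---|
| 0.5 | 1.936 | 48% | 32% |
| 0.8 | 3.098 | 86% | 71% |

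**Step 5. Two brands pooled, no length term.** With 15 v 15 in each length group, length still cancels from the 30 v 30 difference, so there is no bias. The variance estimate, however, absorbs the length effect: its expectation is σ² + (30/29)(L²/4). At L = 0.8 this is 1 + 1.0345 × 0.16 = 1.166, so the standard error is about √1.166 = 1.08 times too large. Simulated type I error is 3.4% at L = 0.8 and about 3% at L = 1.0. At d = 0.5 and L = 0.8, power is 42%, against 48% for the within-length contrast.

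**The case against.** The strongest reply is that no four-product test is written down. Sections 8.2 and 8.7 and the applicator-tube paragraph all speak of two treatments or products. Sections 8.1 and 8.2 size each length group as 15 v 15, which fits a two-group comparison within length. Naming two-group and many-group tests together is common boilerplate, and redundancy does not prove intent. This stands: the four-product null is an inference, and on either two-group reading the inflation disappears.

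Second, ANOVA need not mean one-way. A two-way model with product and length, or a repeated-measures model over the two follow-up visits at which cosmesis is scored, would also be ANOVA. This stands too. The remedy is to specify the ANOVA, not to strike the word.

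Third, the rejection rates depend on an assumed length effect and normal scores. The appendix instrument consists of five Yes/No items, two 1–10 satisfaction ratings and an overall acceptability item, and the documents do not say how these form one score. This limits how far the exact percentages carry over. It does not change the direction of the result.

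Fourth, required summaries such as means, medians and frequency tables could expose a length-driven pattern. They could, but they would not correct the reported p-value.

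What survives is that the text neither excludes the four-product test nor says how incision length enters the comparison.

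**Conclusion.** The cosmesis comparison is under-specified in a way that matters. One permitted reading gives a test that can reject on incision length alone: about 11%, 32% and 71% at length effects of 0.25, 0.5 and 0.8 SD, against a nominal 5%. With no length effect it does not inflate, but it still has less power for a brand difference (32% v 48% at 0.5 SD; 71% v 86% at 0.8 SD). Pooling the two brands without a length term is valid but conservative when length affects cosmesis, at a modest cost in power.

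A reader might infer that the plan commits to a four-product test, or that every listed option has an inflated error rate. The documents support neither. The number of groups is not stated, and the two-group t-test and Mann-Whitney options do not share the inflation.

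The figures rest on 15 per product, normal scores with equal SD, a two-sided 5% level and assumed length effects. Cosmesis is a secondary endpoint, so this is a change that should be made and not one on which the trial's main conclusion turns.

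**What to change.** In the Cosmesis paragraph of Section 8.8.2:

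- Define the treatment comparison as the product effect (OptiClose v Dermabond) from a linear model, that is a two-way ANOVA, with product and incision-length group as factors. If a rank test is used, make it a van Elteren test stratified by length group.
- Report the Secure v Prineo and Rapid v Advanced differences alongside, since the overall effect averages two different product pairs.
- State that a one-way ANOVA or Kruskal-Wallis test across the four products will not serve as the treatment comparison.

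The cost is SAP wording only. No further data or participants are needed, and the length term takes one degree of freedom. The plan gives up a single omnibus p-value over four products, which does not answer the brand question.

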### **Number of Applicator Tubes**

- A Chi-Square test will be used to compare the observed frequencies of number of tubes between the two products. The test statistic is calculated by comparing the observed frequency to the expected frequency under the null hypothesis. The p-value will be obtained to determine the statistical significance of the observed difference.

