**Endpoints:**

*Primary Endpoint:* Incidence of wound edge apposition without dehiscence or need of re-approximation following wound closure.

*Secondary Endpoint:* Secondary endpoints include:

- Surgical Site Infections (SSIs) (criteria defined by the CDC), if applicable
- Inflammatory reactions as calculated by the International Contact Dermatitis Research Group (ICDRG) grading system (see appendix), if applicable.
- Cosmesis as assessed by the Modified Hollander score (see appendix).
- Dry time as objectively measured by an observer/end user.
- Number of applicator tubes/mesh used.

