### **6.2 Post-operative Application of Surgical Site Adhesive**

After the completion of the surgical procedure the surgical site will be prepared in a standard fashion using appropriate layered closure. During this time, the products (Opticlose or Dermabond), will be applied to the surgical site incision. Following the application of the products, the time the products take to dry on the surgical site will be recorded using a stopwatch.

For the mesh group, the stopwatch will begin when the package is opened and once the mesh is laid down for initial application. Once the mesh is appropriately applied, the first time stamp will be recorded. The stopwatch will begin again once the glue has been opened and will stop once the glue has sufficiently covered the mesh for a second time stamp. The stopwatch will then start again, and the applicator will touch the application site at 15 second intervals until no glue is detected on the gloved finger. Once dry, the third and final time stamp will be recorded.

For participants assigned to the glue only group, the stopwatch will begin once the glue has been opened and will stop once the target area has been sufficiently covered for the first time stamp. The stopwatch will begin a second time and the applicator will touch the application site at 15 second intervals until no glue is detected on the gloved finger. Once dry, the second time stamp will be recorded.

The number of applicator tubes used when applying the various products will also be recorded during the product application.

Throughout this process, the circulating nurse will be assessing the participants for potential adverse events related to any surgical site infections or any signs of allergic skin

reactions. If an allergic reaction is detected the assessment will include an International Contact Dermatitis Research Group (ICDRG) grading system (see appendix). Following the completion of the assessment, the participants will be allowed to leave and follow up in their next office visits.

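### The number of applicator tubes is an ordered count, but the plan names only an unordered chi-square test, does not say whether it is run within incision-length group, and gives no rule for small counts

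*Combined protocol and SAP*

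**What the plan says.** The synopsis lists the secondary endpoint as "Number of applicator tubes/mesh used". Section 6.2 says how it is collected: "The number of applicator tubes used when applying the various products will also be recorded during the product application". The raw datum is therefore one whole number per participant.

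Section 8.8.2 gives the whole comparison: "A Chi-Square test will be used to compare the observed frequencies of number of tubes between the two products". It describes the statistic as follows: "The test statistic is calculated by comparing the observed frequency to the expected frequency under the null hypothesis". That is the ordinary Pearson form. No trend, rank or exact test is named for tubes, and no significance level.

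On design, Section 6.1 randomises within incision length. For long incisions "participants will be randomized into the OptiClose Secure group or the Dermabond Prineo group"; for short ones the pair is OptiClose Rapid and Dermabond Advanced. Section 8.2 plans "simple randomization, with 15 participants designated to receive Opticlose and 15 to receive Dermabond" in each length group, and "a total of 60 participants will be required to complete the study, 30 in each incisional length group". The tube paragraph does not mention length group.

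Other secondary endpoints in the same section are better served. Surgical site infection has Fisher's exact test when expected frequencies are low, and cosmesis has a rank test for non-normal data.

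**The concern.** Three gaps meet in one sentence of the plan.

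- **Order.** The Pearson statistic does not change if the tube columns are shuffled. One tube against four counts the same as one against two. With k different counts the test spends k − 1 degrees of freedom on a question that mostly needs one.
- **Length group.** A comparison of the two products could be one 30 v 30 table or two 15 v 15 tables. If long incisions take more tubes whatever the product, a single table adds variation that has nothing to do with product.
- **Sparse tables.** At 15 v 15 a table with several columns will have small expected counts, and no rule says what happens then.

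A real difference in product use could be missed. Even a significant result would not say how many extra tubes one product needs, which is what a user of the endpoint wants to know.

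**Working it through.** **The plan's own figure.** There is none for tubes. The only power figure, in Section 8.1, concerns mean dry time and does not enter this point.

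**Inputs from the documents.** 15 v 15 within each of two length groups, 60 in all; a tube count per participant; a Pearson chi-square.

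**Assumed inputs.** Two-sided alpha 0.05, and every tube distribution below.

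**Step 1: expected counts.** With equal arms, the expected count in a cell is half its column total. At 15 v 15 it is at least 5 only if at least 10 of the 30 participants used that number of tubes.
- Four or more different counts would need 4 × 10 = 40 participants, more than the 30 available, so some cell always falls below 5.
- With three counts, only an exact 10/10/10 split avoids it.
- With two counts it is often avoided. For 80/20 v 40/60, about 15% of simulated tables had a low cell.

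**Step 2: cost of extra degrees of freedom.** A 1-df test with 80% power has noncentrality (1.960 + 0.842)² = 7.85. At the same noncentrality, power falls to 71% with 2 df, 65% with 3 df and 60% with 4 df.

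**Step 3: order alone, within one length group, 15 v 15** (20,000 simulated trials per row).

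| Assumed share using 1, 2, 3… tubes | Chi-square | Wilcoxon | Difference |
|---|---|---|---|
| .8/.2 v .4/.6 | 0.63 | 0.60 | none lost |
| .6/.3/.1 v .25/.4/.35 | 0.47 | 0.58 | 0.11 |
| .5/.3/.15/.05 v .15/.3/.3/.25 | 0.49 | 0.68 | 0.20 |
| .4/.3/.15/.1/.05 v .1/.2/.2/.25/.25 | 0.47 | 0.73 | 0.26 |
| spread only: .1/.8/.1 v .4/.2/.4 | 0.90 | 0.08 | chi-square stronger |

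The largest relative loss here is 0.26 / 0.73 = 36%.

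**Step 4: order and length group together.** Assumed glue-only use: 60/30/10% on 1 to 3 tubes v 35/40/20/5% on 1 to 4. Assumed mesh use: 5/25/40/20/10% on 1 to 5 v 0/10/35/35/20%.

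| Test | Power |
|---|---|
| Pooled chi-square, 30 v 30 | 16% |
| Pooled Wilcoxon, 30 v 30 | 34% |
| Wilcoxon stratified by length | 61% |
| Mesh only, 15 v 15: chi-square, Wilcoxon | 17%, 36% |
| Glue only, 15 v 15: chi-square, Wilcoxon | 18%, 32% |

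Of the 45-point gap between the first and third rows, 34 − 16 = 18 points come from using the order and 61 − 34 = 27 from stratifying. With no product difference, the pooled chi-square rejects in 2% to 3% of trials and the stratified test in about 5%.

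Hand check of the 61%:
- Glue-only means are 1.50 and 1.95, variances 0.450 and 0.7475. The difference is 0.45, with squared standard error (0.450 + 0.7475)/15 = 0.080.
- Mesh means are 3.05 and 3.65, variances 1.0475 and 0.8275. The difference is 0.60, with squared standard error 1.875/15 = 0.125.
- The average difference is 0.525, with standard error ½√(0.080 + 0.125) = 0.226. The ratio is 2.32, and Φ(2.32 − 1.96) = 0.64, close to the simulated 61%.

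**Step 5: how far pooling matters.** With .6/.3/.1 v .25/.4/.35 in both length groups, and mesh shifted up by a set number of tubes:

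| Mesh uses | Pooled chi-square | Pooled Wilcoxon | Stratified Wilcoxon |
|---|---|---|---|
| same | 0.79 | 0.87 | 0.87 |
| 1 more | 0.55 | 0.76 | 0.88 |
| 2 more | 0.30 | 0.35 | 0.87 |
| 3 more | 0.56 | 0.09 | 0.87 |

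A rank test without stratification is therefore not a safe substitute.

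**The case against.** The best case against the point is that it is easily overstated. Four stronger readings are tempting, and the documents support none of them.

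- **That most of the power is lost at 15 v 15.** In Step 3 the loss ran from none to 36% of the power. In the smaller shift of Step 4 it was about half for mesh (17% v 36%) and less for glue-only (18% v 32%). With two observed counts nothing is lost, and for a difference in spread the chi-square wins clearly.
- **That the plan pools the length groups.** The tube paragraph does not say so. The synopsis describes two separate arms with their own product pairs, and Section 8.1 works at 15 v 15. Separate tests are a fair reading, and on that reading the 16% v 61% contrast does not apply.
- **That sparse cells inflate false positives.** In the simulations with no product difference the chi-square was, if anything, conservative: 4% at 15 v 15 with three counts, and 2% to 3% when pooled over groups with different tube use.
- **That the plan offers no estimate at all.** Section 8.7 promises means with 95% confidence intervals for continuous variables. If tubes are summarised as numbers, each product gets a mean and interval. What is missing is the difference between products with its interval.

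A stratified rank test also has a weakness. If the two product pairs differ in opposite directions, the effects cancel: its power was 0.03 in such a scenario, against 0.63 for the pooled chi-square. Results within each length group are needed beside the combined test.

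What stands is that the order is unused, length group is unaddressed, and no small-count rule is given for this endpoint although one is given for infections.

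**Conclusion.** The point holds as a gap in the analysis of one secondary endpoint. That the data are ordered, that the named test ignores order, and that length group and small counts are not covered can all be read from the text without assumptions. So can the result that four or more different counts at 15 v 15 must give an expected count below 5.

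The size depends on assumed tube distributions and a two-sided 0.05 level. For a shift in tube use with three or more counts, the loss is roughly 10 to 26 power points at 15 v 15. It can be larger if length groups with different tube use are pooled, and it vanishes if only two counts occur.

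Severity is minor: the primary endpoint is untouched, and the plan sets no power target or decision rule for tubes.

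**What to change.** In Section 8.8.2, replace the chi-square for tubes with a Wilcoxon rank-sum test stratified by incision-length group (van Elteren), and state the significance level and sidedness. Report the difference in mean tubes per participant between products, with a 95% confidence interval, within each length group and combined. The within-group results guard against effects that run in opposite directions. Keep the frequency table as a description.

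Under the Step 4 assumptions the combined interval would be about ±2.0 × 0.226 = ±0.45 tubes, which tells a reader more than a p-value.

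The cost is a sentence or two in the plan and a standard SAS procedure. The data are already collected, and the sample size does not change.
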